The inclusion/exclusion criteria for Study 2 (the survey data collection on 250 participants) will be more selective. These participants will be consumers seeking services from MHA, and more specifically those who based on either of these screeners have identified as experiencing at least moderate symptoms of depression and/or anxiety. Participants will be 18 and older with little to no experience with the concept of cognitive reframing.

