## **Randomization sequence**

The drafted randomization sequence is outlined on the MHA SMART Flow.pdf uploaded to zipline. Participants will be randomized first between a standard demographics survey to start or demographics along with a mini quiz focusing on asking a participant's primary website action intention (e.g., reading more about depression, connecting with therapists, using a DIY tool) and perceived need to do something to improve their mental health. Participants will then be randomized to types of screening results pages, with combinations of tailored responses and resources based on their responses to the demographics quiz and/or the mini quiz. For instance, if the participant chooses to continue to visit further content, they will be randomized to conditions of different presentations of a DIY question or tool on the page. Length of engagement, bounce rates, and other variables listed under metadata collection will be used to examine the impact of tailoring on engagement, which conditions and combinations of conditions result in increased engagement, and how the use of DIY tools impact engagement.

## Study 2

As previously proposed in Aim 3, we have developed an AI tool that uses machine learning / NLP / AI methods to personalize and tailor an intervention to improve engagement and completion outcomes. We focus on a specific, popular DIY tool (~10,000 users /month) that teaches cognitive restructuring. Our pilot work found that (1) engagement and completion rates on DIY tools can be low, and (2) a pilot AI tool had significantly higher engagement and completion rates. These differences may arise due to AI support, UI/UX/design differences, other factors, or a combination thereof. Additionally, the efficacy of the digital tool to improve mental health functioning is unknown. Study 2 will recruit 300 participants who will be randomly assigned to one of three groups for a longitudinal month-long study: twice-weekly DIY tool use with AI, without AI, or a control group.

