## **Recruitment Procedures**

Potential participants will be shown an invitation to participate in this portion of the study and displayed on the screening results page for users after the PHQ-9 and GAD-7 mental health tests. If consumers are interested in learning more, they can respond to the invitation by clicking on a link, which will direct them to a landing page (displayed via REDCap survey) with more information about the study and the screening survey.

Screens/Surveys: All measures in this section will be completed using REDCap – refer to DOC: DIY Study – Measures for all measures listed in this section, and refer to DOC: Demographic questions for the demographics measure. Participants will receive links to complete these surveys via email and/or text message using Twilio, a REDCap extension that allows for SMS communication with participants. Participants will complete an initial screening assessment to determine eligibility, and then complete the same list of measures for 4 weeks while using intervention (consistent to each condition), an exit survey at week 5 and follow up measures consistent with the weekly measures at week 8 follow up. All participants will be asked to complete the demographics measure in addition to the measures included in the first week's battery of assessments.

Participants will be asked to complete the following measures in the screener:

- PHQ-9

- GAD-7
- Hopefulness Item
- Emotion Mechanisms

At the end of weeks 1-4 and week 8 follow up, participants will be asked to complete the following measures, some measures adjusted depending on condition:

- Questions Post DIY AI [DIY Tool, AI condition ONLY]
- PHQ-9
- GAD-7
- Hopefulness Item
- Emotion Mechanisms
- Competencies of Cognitive Therapy Scale Self Report
- Tool Use (sustain) [DIY Tool, No AI condition ONLY WEEKS 1-4, BOTH DIY TOOL CONDITIONS at WEEK 8]
- Tool Use (AI) [DIY Tool, AI condition ONLY, JUST WEEKS 1-4]

Demographics Measure (just week 1)

At week 8 only, participants will be asked the following questions (in addition to those previously approved):

- What is your total annual household income? (Less than \$20,000; \$20,000 \$39,999; \$40,000 \$59,999; \$60,000 \$79,999; \$80,000 \$99,999; \$100,000 \$149,999; \$150,000 or more; Prefer not to answer)

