ENHANCING ENGAGEMENT WITH DIGITAL MENTAL HEALTH CARE

STUDY00010958

07/03/2024

NCT04507360

Aim 3B Statistical Analysis Plan. For Study 1, all research questions were examined via logistic regressions. We assessed whether participants' first condition (i.e., demographics survey or Next Steps survey) predicted the odds of disengagement. Within participants who completed the demographics survey, we examined whether the odds of disengaging and clicking a featured resource on the screening results page significantly differed for participants in the Tailored Resources to Demographics condition compared to control (i.e., Generic Response + Generic Resources). Within participants from the Next Steps survey condition, we tested whether engagement significantly differed for participants shown Tailored Response + Generic Resources, Generic Response + Tailored Resources to Desired Resources, and Tailored Response + Tailored Resources to Desired Resources compared to control. We aimed to identify the optimal tailoring strategy by comparing engagement across all tailoring conditions, with Tailored Resources to Demographics set as the reference group. For Study 2, research questions were examined via t-tests and Cohen's d effect sizes comparing engagement, short-term restructuring effectiveness, longer-term effectiveness (e.g., skill acquisition, reductions in depression and anxiety), and heterogeneous treatment effects by condition (i.e., control, DIY tool without AI, and DIY tool with AI).

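### Study 2 names no primary test and no multiplicity control across three arms, at least five outcomes and five follow-up surveys, so its overall false positive rate is well above 5% by an amount the SAP leaves open

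*SAP*

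**What the plan says.** The SAP is a single paragraph, and Study 2 takes up one sentence of it. It states that "research questions were examined via t-tests" and Cohen's d, applied to engagement and short-term restructuring effectiveness, and continues with "longer-term effectiveness (e.g., skill acquisition, reductions in depression and anxiety), and heterogeneous treatment effects by condition", the conditions being "i.e., control, DIY tool without AI, and DIY tool with AI". The longer-term outcomes are introduced as examples, so the list is open-ended.

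Protocol section 5.1, in the survey schedule for Study 2, says: "At the end of weeks 1-4 and week 8 follow up, participants will be asked to complete the following measures". The list that follows includes PHQ-9, GAD-7 and the self-report scale of cognitive therapy skills. That gives five post-baseline occasions. The SAP does not say which of them are tested.

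On size, section 5.1 says "Study 2 will recruit 300 participants who will be randomly assigned to one of three groups", while section 2.1 refers to "the survey data collection on 250 participants". No allocation ratio is given.

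For Study 2, neither document states a significance level, a primary outcome, a primary contrast, a primary time point, a testing order, an overall three-arm test or a multiplicity adjustment.

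**The concern.** Protocol section 5.1 says it is not known whether the digital tool improves mental health functioning, so Study 2 is where an efficacy claim would come from. Three arms allow three pairwise tests per outcome. These multiply over at least five outcomes, up to five occasions and an unspecified set of subgroups. With no test singled out in advance, a favourable result on any outcome, week, contrast or subgroup could be presented as the finding, and a reader could not tell a planned result from a selected one. The nominal 5% level would then not describe the error rate of the claim.

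**Working it through.** The documents give no alpha, power or sample-size calculation, so there is no planned figure to reproduce.

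**Inputs from the documents.** Three arms, hence 3 possible pairs. Five outcomes named in the SAP. Five post-baseline occasions (protocol 5.1). A target of 300 participants (protocol 5.1 and 2.7).

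**Assumptions.** Two-sided 0.05 per test. Equal allocation, 300 / 3 = 100 per arm. No true differences. Between-outcome correlation from 0.3 to 0.7, with correlation over time from 0.5 to 0.8 alongside it.

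**Step 1: count the tests.**
- Full grid: 3 pairs x 5 outcomes = 15 per time point; x 5 time points = 75.
- Reduced grid, with engagement and short-term effectiveness compared only between the two tool arms: 2 x 1 + 3 x 3 = 11 per time point; x 5 = 55.
- Expected false positives on the full grid: 15 x 0.05 = 0.75 at one time point; 75 x 0.05 = 3.75 at five.

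**Step 2: independence formula.** The chance of at least one false positive in k independent tests is 1 - 0.95^k.
- k = 3: 14.3%
- k = 11: 43.1%
- k = 15: 53.7%
- k = 75: 97.9%

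These overstate the rate, because pairs share arms and outcomes and occasions are correlated.

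**Step 3: simulation with shared arms and correlation.** Normal data are drawn for three arms of 100 with no differences, every pair is tested at 0.05, and the runs with at least one rejection are counted.

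| Family tested | Tests | Outcome correlation 0.7 | Outcome correlation 0.3 |
|---|---|---|---|
| One outcome, three pairs | 3 | about 12-13% | about 12-13% |
| Reduced grid, one time point | 11 | about 29% | about 37% |
| Full grid, one time point | 15 | about 33% | about 45% |
| Reduced grid, five time points | 55 | about 55% | about 83% |
| Full grid, five time points | 75 | about 63% | about 90-91% |

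Separate runs of the same set-up differ by one to three points, which is simulation error. The rate hardly depends on the number per arm, so the 250 versus 300 conflict does not change this table.

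**Step 4: sensitivity.**
- With outcome correlation 0.9, the 15-test family gives 23%. With both correlations 0.9, the 75-test family gives 42%.
- Adding one two-level subgroup to the 15 tests, with each contrast repeated within each half, gives 60% to 75% for outcome correlations 0.7 to 0.3.

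**Step 5: false positives that favour the AI tool.** One third of the contrasts (tool without AI versus control) do not involve the AI tool, and half of two-sided errors on the others go against it. Counting only rejections in favour of AI gives about 12-19% at one time point and about 25-50% at five.

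**The case against.** The strongest reply is that the large figures rest on tests the SAP never lists. The survey schedule is a plan for collecting data, not for testing it. The SAP also does not say that the tests are unadjusted; that is inferred from its silence. Nor are three-arm contrasts assured for every outcome. Section 5.1 describes tool metadata for the two tool arms and none for control, although the dosage item in section 5.4 also mentions the psychoeducation material. The post-tool questionnaire is given to the AI arm only. All of this stands, which is why the reduced grid is shown and the rates are given as conditional ranges.

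Two stronger readings are tempting. A reader might infer that a false positive is more likely than not. The documents do not support that as a general statement: at a single time point without subgroups the rate stays below 50% even on the full grid. It passes 50% only if testing is repeated over several time points or subgroups, and the SAP does not say that it is. A reader might also infer that any chance finding would count as an effect of the AI tool. Step 5 shows that this is true of only some of them.

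None of this answers the narrow point. Even one outcome with three pairwise tests exceeds 5%, and nothing in either document says which test carries the claim.

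**Conclusion.** The point holds in conditional form. No primary test or multiplicity control is stated for Study 2, and the overall error rate is above 5% in every scenario examined. It runs from about 12-13% in the smallest family, through about 29-45% for five outcomes at one time point, to about 55-91% if all five time points are tested. These figures assume 0.05 per test, no true differences and moderate correlations. They describe the chance of any false positive, not of one favouring the AI tool. The SAP cannot be used to pin the rate down further, because it does not list its contrasts, time points or subgroups.

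**What to change.** The remedy depends on timing. The SAP is dated 07/03/2024 and written in the past tense, so the analyses may already have been done.

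- **If the outcome data have not been examined:** name one primary outcome and time point from those already collected. The choice is the sponsor's; entry is allowed on either the depression or the anxiety score, and the tool is also meant to raise engagement, so no single measure is the obvious one. Test the three arm contrasts on it in a stated order at 5% each, stopping at the first non-significant result, or apply Holm across the three pairs. Report everything else as exploratory, with effect sizes and 95% intervals.
- **If the analyses are done:** do not name a confirmatory primary now. List every Study 2 test performed, then either give Holm-adjusted p-values over that family or label all results exploratory. Do not base an efficacy claim on one nominal p-value.

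In both cases, state alpha, the contrasts, the time points and the subgroups, and reconcile 250 with 300.

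The cost is SAP wording and reporting, with no new data. Fewer results carry confirmatory status, and adjusted tests lose power. As an illustration, take an assumed d = 0.4, 100 per arm and no dropout. Power is 81% at 0.05, which is what the first contrast in a fixed order keeps. It is 67% at 0.05/3 = 0.0167, Holm's first threshold for three pairs, and 46% at 0.05/15 = 0.0033. At 0.05, power falls to 73% with 83 per arm (about 250 / 3) and to 65% with 70 per arm.

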**AIM 3b.** Using a SMART designed trial of 10,000 TS consumers, of which 250 will participate in a survey after they discontinue treatment for two weeks, we will compare effective engagement strategies tailored to subtypes developed under Aim 2 to study the mediated impact of engagement strategies on consumer mental health outcomes (e.g. PHQ9). This activity will occur in Y04 of the partnership. We will prospectively recruit participants into micro-randomized and SMART trials to collect additional survey information on participants about self-efficacy (task, coping and recovery), perceived risk/needs, planning skills and anticipated outcomes. We will determine if engagement strategies targeted to consumer engagement subtype will enhance engagement and in turn result in improved clinical outcomes. These will be compared to generic strategies that are not subtype targeted.

Update August 2023: Talkspace will no longer be involved for year 4 of the project and will not complete activities for aim 3B. All aim 3B activities will occur with MHA, broken down into two parts: (1) a Sequential Multiple Assignment Randomized Trial (SMART) of a projected 50,000+ participants and (2) a DIY tool longitudinal randomized control trial (RCT). This is possible with no change in our aim purpose or final budget.

(1.6) Study design. Provide a one-sentence description of the general study design and/or type of methodology.

Your answer will help HSD in assigning applications to reviewers and in managing workload. Examples: a longitudinal observational study; a double-blind, placebo-controlled randomized study; ethnographic interviews; web scraping from a convenience sample of blogs; medical record review; coordinating center for a multi-site study.

This is a prospective, longitudinal and iterative study, divided into three phases:

Phase 1: Data analysis of existing data from 100,000 MHA and TS of data collected between 2020 and the end of Y01 of the project.

Phase 2: Building off findings from Phase 2, rapid and iterative micro-trials (MRTs) of engagement strategies Phase 3: a culminating sequential multiple assignment randomized trial (SMART) used to optimize match between client subtypes identified in Phase 2 and engagement strategies identified in Phase 1.

This initial IRB application is for Phase 1 activities only. Subsequent modifications will be submitted for Phase 2 and Phase 3 once appropriate.

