## **Screens & Surveys**

Both MHA and TS collect information from consumers about their demographics such as age, gender, marital status, race/ethnicity, income status and education. MHA and TS also collects these symptom measures at initial engagement with services:

• PHQ9 (depression),

- GAD7 (anxiety),
- Prodromal Questionnaire-Brief Version (PQ-B; psychosis);
- Brief Bipolar Test;
- SWED (eating disorders),
- PC-PTSD (PTSD),
- CAGE-AID (Substance Use Disorder);
- Work Health Survey,
- caregiver status, and the
- Duke Social Support Scale, a measure of perceived social support.

These variables will be used to characterize consumers, and may serve as moderators of engagement (Aims 1, 2 and 3a) and clinical outcomes (Aim 3b). These measures have been uploaded to Zipline.

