#### **Randomization Procedures**

Once consenting to the study, upon beginning the REDCap screening survey, potential participants will automatically be randomly assigned to one of three conditions. This random assignment will not impact their screening process, eligibility, or the consent process. Their randomly assigned condition will not be revealed to them until after they consent to the study. Upon their consent, the information will be delivered to them via email, informing them of their assigned condition, outlining the study tasks and payment structure.

The three conditions are as follows: Control condition with psychoeducational reading material, a DIY worksheet, or a DIY tool with artificial intelligence, and are all concerned with the idea of thinking traps and learning how to apply the concept of cognitive reframing to situations in one's own life. Folks in both DIY tool conditions will be prompted to use their tools 3x a week, and all participants will be asked to respond to weekly surveys for the duration of 4 weeks.

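### The Study 2 SAP examines heterogeneous treatment effects with t-tests and Cohen's d by condition, which do not test whether the effect differs between participants, whether run on the whole sample or within subgroups

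*SAP*

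**What the plan says.** The Study 2 analysis plan is one sentence of the SAP. It states that "research questions were examined via t-tests and Cohen's d effect sizes comparing engagement", short-term and longer-term effectiveness and, as the last item, "heterogeneous treatment effects by condition (i.e., control, DIY tool without AI, and DIY tool with AI". For Study 2 it gives no moderator, subgroup, cut-point, interaction term, regression model or multiplicity rule. For Study 1 the same paragraph does name a regression model.

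The nearest protocol text is in section 5.1, Phase 1, Screens & Surveys. There, platform demographics and a list of symptom and support measures "may serve as moderators of engagement (Aims 1, 2 and 3a) and clinical outcomes (Aim 3b". Study 2 falls under that aim, since the August 2023 update in section 1.5 says "All aim 3B activities will occur with MHA, broken down into two parts", the second part being the DIY tool trial. The Phase 1 text is permissive: it selects no variable for Study 2 and describes no test. The Study 2 procedures in section 5.1 and the variable list in section 5.4 add nothing on moderation.

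**The concern.** A two-sample t-test, or Cohen's d, between conditions estimates an average difference. Whether that difference varies with a participant characteristic is a separate question. It needs a named characteristic and a direct contrast of the effect across its levels. The method given for this item supplies neither.

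The SAP sentence can be read in two ways, and both lead to trouble. If the t-tests were run on the whole sample, the result says nothing about heterogeneity. If they were run within subgroups and their significance was compared, identical effects would often look different. Either way, a reported heterogeneity result would not answer the question the SAP sets, and a reader could not tell which variables had been tried.

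**Working it through.** The documents give no alpha, power, effect size or SD for Study 2, so there is no stated figure to reproduce.

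**Inputs from the documents.** Three conditions. 300 participants (protocol 2.7 and 5.1), or 250 (protocol 2.1 and 4.1), so 300/3 = 100 or 250/3 = 83.3 per arm.

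**Assumptions.** Equal arms, outcome SD 1, two-sided alpha 0.05, moderator split 50/50, no dropout.

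**1. If the t-test is on the whole sample (one pair of arms, 100 per arm, simulated).**
- Effect 0.4 SD in both halves: about 80% significant, mean d 0.40.
- Effect 0.8 SD in one half and 0 in the other: 76 to 78% significant across separate simulations, mean d 0.38 to 0.39.
- The average effect is the same, (0.8 + 0)/2 = 0.4. d falls slightly because mixing two effects adds 0.4² = 0.16 to the treated-arm variance. The pooled SD is √((1.16 + 1)/2) = 1.039, and 0.4/1.039 = 0.385.

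**2. If t-tests are run within two equal subgroups with the same true effect.** With m per arm per subgroup, the noncentrality is d√(m/2). If each test has power p, the chance that exactly one is significant is 2p(1 − p).

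| d | p, m = 50 (N=300) | exactly one | p, m = 41.7 (N=250) | exactly one |
|---|---|---|---|---|
| 0.3 | 0.318 | 43% | 0.272 | 40% |
| 0.4 | 0.508 | 50% | 0.438 | 49% |
| 0.5 | 0.697 | 42% | 0.616 | 47% |
| 0.6 | 0.844 | 26% | 0.772 | 35% |

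There is no heterogeneity in any row. A single interaction test would reject in about 5%.

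**3. Power of the analysis recommended below.** Four screener moderators, one score each (assumed), first Holm step 0.05/4 = 0.0125. The joint 2-df F test has noncentrality λ = n × var(moderator) × sum of squared deviations of the arm-specific moderator effects. A 50/50 binary moderator has variance 0.25. If one arm differs by D, the sum is 2D²/3. If the effects are graded (0, D/2, D), it is D²/2.

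| n per arm | D | λ, one arm differs | power | λ, graded | power |
|---|---|---|---|---|---|
| 100 | 0.8 | 100 × 0.25 × 0.427 = 10.67 | 67% | 100 × 0.25 × 0.320 = 8.00 | 51% |
| 83.3 | 0.8 | 8.89 | 57% | 6.67 | 41% |
| 100 | 0.4 | 2.67 | 13% | 2.00 | 10% |
| 83.3 | 0.4 | 2.22 | 11% | 1.67 | 8% |

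**4. Which variables are safe as moderators.** Protocol 5.1 (Study 2) says "Participants will be asked to complete the following measures in the screener" and lists PHQ-9, GAD-7, the Hopefulness item and Emotion Mechanisms. Protocol 8.2.b puts consent after the screener, and 5.1 states that "Their randomly assigned condition will not be revealed to them until after they consent to the study". These four measures therefore cannot be influenced by knowledge of the condition. The demographics form ("Demographics Measure (just week 1") and the income item ("At week 8 only, participants will be asked the following questions") come after the condition is known, so whether they are completed may depend on the arm.

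**The case against.** The best defence is that one past-tense summary sentence is being made to carry too much. It does not say how the heterogeneity question was handled, and interaction models may have been run without being mentioned. This stands in part. A reader might infer that the whole-sample t-test was itself reported as the heterogeneity analysis, or that significance was compared between subgroups. The SAP states neither, so both illustrations are conditional on the reading. The point survives because t-tests and Cohen's d are the only method stated, and neither reading tests a difference in effects.

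A reader might also infer that no candidate moderators appear anywhere. The Phase 1 list shows otherwise; what is missing is a selection and a test.

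Nor should the remedy be oversold. For one pair of arms, one moderator and alpha 0.05, a 1-df interaction test detects the 0.8 SD contrast in about 80%. The joint test adjusted over four moderators has only the power shown in the working. Using fewer moderators helps: one moderator at alpha 0.05 gives 29% power for a 0.4 SD difference on a single contrast at 100 per arm (0.4/√(8/100) = 1.41, against a critical value of 1.96). Testing all four screener measures is a choice, not a necessity.

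Finally, heterogeneity is the last item in the list and is not designated primary, and a moderator chosen now cannot be prespecified. This bears on how much weight the point carries, not on whether it is right.

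**Conclusion.** The concern holds in this limited form: the only stated method for the heterogeneity question does not test it on either reading, and no moderator is selected. On the whole-sample reading, a uniform effect and one confined to half the participants give nearly the same result. On the within-subgroup reading, equal effects produce one significant and one non-significant subgroup in 26 to 50% of trials at N=300, and in 35 to 49% at N=250. These sizes rest on the assumed SD, alpha, effects, equal split and absence of dropout. The documents do not establish that an invalid heterogeneity result was obtained. The average-effect comparisons between conditions are unaffected.

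**What to change.** State what was done for heterogeneity, then base any heterogeneity statement on the following.

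- **Model.** For each outcome and moderator, a regression on condition, the screener value of the outcome where one exists, the moderator, and condition × moderator. If the moderator is that screener value, enter it once.
- **Moderators.** Screener PHQ-9, GAD-7, Hopefulness and Emotion Mechanisms, kept continuous. If the week-1 demographics or week-8 income are used, report how many per arm lack them.
- **Time point.** One stated time point per outcome, the same as for that outcome's main comparison. The scales recur at weeks 1 to 4 and week 8, so without this the number of tests is undefined.
- **Reporting.** Interaction estimates with 95% CIs, a joint test per moderator (2 df, or 1 df where an outcome exists in two arms only), the number of tests, and the multiplicity adjustment, for example Holm over the moderators within each outcome.
- **Interpretation.** Label the analysis exploratory, and post hoc unless earlier documentation exists. Do not compare significance between subgroups, and do not read a null result as no heterogeneity.

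If this is not done, withdraw the heterogeneity claim.

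The cost is SAP wording and re-run models, with no new data collection. The downside is low power, as shown in the working. If Emotion Mechanisms yields several scores, there are more tests and the power is lower still.
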